2.3 Stereotactic Body Radiotherapy in Oligometastasis

However, nephrectomy and metastasectomy are invasive procedures with risk for perioperative morbidity. This is particularly the case for patients having comorbid conditions or requiring more extensive surgeries. Also, not all patients are candidates for resection due to invasion of adjacent structures by tumors. Radiotherapy is an alternative modality used for the treatment of radiographically visible tumors. Although RCC has historically been thought to be resistant to conventionally fractionated radiotherapy (1.8-2 Gy per fraction) [32-34], multiple series suggest it may be sensitive to higher fraction sizes of radiotherapy (stereotactic radiotherapy) [35-38].

Stereotactic Radiotherapy is the use of high doses of radiation per fraction to deliver ablative doses of radiation to lesions throughout various body sites. Stereotactic radiotherapy administered in one fraction, commonly to intradural lesions, is usually described as stereotactic radiosurgery (SRS). Stereotactic radiotherapy administered over 1-5 fractions to extracranial sites in > 5 Gy per fraction is known as stereotactic body radiotherapy (SBRT).

There is considerable experience with SBRT in medically inoperable early stage lung

cancers [39-42], and an increasing body of evidence suggesting a role of SBRT in oligometastatic cancers. The ablative doses of SBRT in the oligometastasis setting have allowed for local control rates approaching 90% in such series [43-46].

Based on retrospective series suggesting a local control rate with SBRT of 87-98% [35, 47-49], a prospective Phase II Swedish study assessed the role of SBRT in 30 patients with metastatic or inoperable primary tumor RCC [38]. Patients were treated with 20-50 Gy given in 2-5 fractions to involved sites. With median follow-up of 52 months, 21% of patients had complete regression of tumor, 31% had a partial response, and 27% had stable radiographic size. The rate of local control for all treated lesions was 98%, and the overall survival for the entire cohort was 32 months. This suggests SBRT can be effective to control RCC. Additionally, retrospective series also suggest limited toxicity with SBRT [37, 45, 47, 49-51].

There are numerous SBRT fractionation regimens that have been evaluated [38, 39, 41, 52-54]. However, the optimal dose and number of fractions of SBRT are unknown. A prior phase I dose escalation trial was performed to evaluate SBRT for oligometastatic cancer at the University of Chicago. This study used a modified Fibonacci dose escalation to identify the maximal safe organ-specific doses that could be delivered in a 3-fraction SBRT regimen [45]. However, the patient cohort in this study was heterogeneous, with only 8 of 61 patients (13%) having renal cell malignancies. Additionally, different doses for each specific organ of involvement were used. This approach is more complex and may be more difficult to implement in subsequent trials and in the community. In addition, 5-fraction SBRT may be better tolerated by critical structures, particularly for tumors near gastrointestinal critical structures. For primary tumors, Wersall et al used 40 Gy in 5 fractions for tumors up to 10 cm in size [47]. Videtic et al evaluated the use of a SBRT regimen of 50 Gy in 5 fractions in medically inoperable non-small cell lung cancer and found a 3 year local control rate of 94.4% and acceptable toxicity [41]. In addition, 50 Gy in 5 fractions is the starting dose and fractionation of RTOG 0813, a Phase I/II dose escalation study of SBRT in non-small cell lung cancer currently open in multiple centers. Typically, the dose and fractionation schemas used to treat metastatic lesions in the lung are similar to those used in primary lung cancer. The 50 Gy in 5 fractions schema also has the benefit of being tolerable in multiple organ sites other than the lungs [55]. Thus, 50 Gy in 5 fractions was selected as the preferred schema in our trial, with 40 Gy in 5 fractions used as an alternative dose when normal tissue constraints cannot be met using the preferred dose.

Most series suggest a favorable risk profile of SBRT when keeping doses to normal tissues within established dose constraints. However, there are a few case reports of patients treated with radiotherapy (both SBRT and conventionally fractionated radiotherapy)[56-60]. The agent that appears to be most commonly associated with severe toxicity is bevacizumab; several larger series have demonstrated safety when combining tyrosine kinase inhibitors (e.g. Sunitinib, Pazopanib) with radiation therapy [61-64]. Therefore, this study will exclude men treated with bevacizumab prior to enrollment, but will allow patients treated with other tyrosine kinase inhibitors to be eligible for this trial.

2.4 Rationale for current study

The above evidence suggests a role for aggressive local treatment of metastatic lesions in RCC. We hypothesize that SBRT can be safely and effectively delivered in patients with oligometastatic RCC. Results will inform the development of a larger, multicentric trial.

This study will evaluate a 5-fraction regimen in patients who have a histology diagnosis of metastatic RCC with 5 or fewer sites of disease. All organs of involvement will receive 5 fractions with a preferred dose of 50 Gy in 5 fractions. This pilot study will evaluate the ideal candidates for this approach, the likely accrual and accrual rate of a phase II study, and the optimal dosimetric and dose/fractionation considerations in pursuing this approach. In addition, this study will allow for the collection of data to possibly refine eligibility and treatment

delivery for future studies, and help determine sample size calculations for the next generation trials. Subsequent testable hypotheses could include randomized comparisons of SBRT +/- concurrent molecularly targeted systemic therapy, observation +/- SBRT, or systemic therapy +/- SBRT.

2.4.1 Rationale for Secondary Objectives

Patients with sites of metastatic disease commonly present with pain from these lesions. Conventional radiotherapy can offer palliation for most patients, but the durability of pain control is variable. In order to describe the clinical efficacy of this treatment approach, we will also evaluate objective response rate, treated lesion control, and the patterns of failure.

3. PATIENT SELECTION

3.1 Eligibility Criteria

- 3.1.1 Patients must have histologically or cytologically confirmed metastatic or recurrent RCC (any histologic subtype).
- 3.1.2 Patients must have between 1 to 5 new or recurrent lesions suspicious for metastatic RCC on diagnostic imaging.
 - 3.1.2.1 Each extracranial lesion must be ≤ 6 cm and amenable to SBRT or surgical excision.
 - 3.1.2.2 Patients must have 3 or fewer brain metastases, of size ≤ 4 cm.
 - 3.1.2.2.1 Brain metastases must be treated prior to enrollment in the study. The modality of treatment of brain metastases can include surgical resection, whole brain radiotherapy, stereotactic radiosurgery, or any combination of the above.
 - 3.1.2.3 Patients who have an intact unresected primary tumor should be considered for radical nephrectomy and primary resection prior to enrollment in the study. If the patient is not eligible for surgical resection, the primary tumor must be amenable to SBRT or RFA. Generally, this will be defined as a primary tumor <10 cm in size or a primary lesion which can be treated to a dose of ≥ 8 Gy x 5 without excessive perceived risk of toxicity.
- 3.1.3 Patients must have had at least a CT of the chest, abdomen, and pelvis within 4 weeks of registration in the trial. CT or MRI of the brain is only required in the presence of neurologic symptoms.
- 3.1.4 Patients must have had no radiotherapy, immunotherapy, chemotherapy or therapy with targeted agents within the last 1 month.
- 3.1.5 Patients may not have had prior bevacizumab, based on case reports of tracheo-esophageal fistula in patients treated with bevacizumab and radiotherapy [58, 59].
- 3.1.6 Age ≥ 18 years. Because of the risk of adverse events in patients <18 years of age, children are excluded from this study, but will be eligible for future pediatric SBRT trials.

- 3.1.7 ECOG performance status ≤ 2 (see Appendix A).
- 3.1.8 Life expectancy of ≥ 3 months.
- 3.1.9 Patients must have normal organ and marrow function within 30 days of registration, as defined below:
- absolute neutrophil count $\geq 500/\text{mcL}$
 - hemoglobin $\geq 8.0 \text{ g/dL}$
 - platelets $\geq 50,000/\text{mcL}$
 - total bilirubin within normal institutional limits
 - AST(SGOT)/ALT(SGPT) $\leq 3X$ institutional upper limit of normal if liver metastases are present
- 3.1.10 Women of childbearing potential must have a negative pregnancy test within 14 days of registration.
- 3.1.11 Patients must have the ability to understand and the willingness to sign a written informed consent document.

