TITLE: A PILOT STUDY OF STEREOTACTIC BODY RADIOTHERAPY (SBRT) IN OLIGOMETASTATIC RENAL CELL CARCINOMA

Principal Investigator: [name].
Department of Radiation and Cellular Oncology
University of Chicago Medical Center
[name]
[name]
[contact]
[contact]
[contact]

Sub-Investigators:

Radiation Oncology
[name] PHD
[name]
[name]

Urology
[name]
[name]
[name]

Medical Oncology
[name]
[name]
[name]
[name]

Biostatistics
[name]

Research and Nursing Support
[name]
[name]

Funding: Internally funded through the Department of Radiation and Cellular Oncology

Sponsor: [name]./University of Chicago

Intervention: Stereotactic Body Radiotherapy to all sites of disease

Protocol Version: 2.0

Protocol Version Date: 08.05.19

STUDY SUMMARY SCHEMA

Patient population:

- Histologically or cytologically diagnosed renal cell carcinoma (any histologic subtype)
- No systemic therapy or radiation therapy within 1 month prior to enrollment
 - No prior bevacizumab
- ECOG performance score 0-2 and ≥ 3 month life expectancy
- 1-5 sites of metastatic (or recurrent) disease, each ≤ 6 cm and amenable to SBRT
 - Up to 3 brain metastases may be included

Treatment:

- 25 patients will be enrolled and treated according to protocol guidelines for SBRT
- Brain metastases must be addressed prior to enrollment
- Day1 : Begin SBRT to all involved sites, 5 fractions on non-consecutive days
- Enrollment halted if there are two grade 4 toxicities within the first 2 patients, three within the first 14 patients, or 4 within the first 25 patients

Follow-up:

- Clinical follow-up to assess CTC toxicity and disease control, monthly up to 3 months, then q3 months up to 1 year
- CT chest/abdomen/pelvis q3 months up to 1 year
- Off protocol therapy at clinician discretion but no earlier than 4 weeks after start of SBRT

Required Sample Size: 25 patients would be required

Study Center: University of Chicago Medical Center, Chicago, IL

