10. STUDY CALENDAR

Baseline CBC, serum chemistry, and pregnancy test (if indicated) are to be conducted within 30 days prior to study registration. Scans and x-rays must be done ≤6 weeks prior to study registration.

	Pre-Study	Wk 1	Wk 2	Wk 3-4	1 Mo Post-RT [^]	2 Mo Post-RT [^]	3 mo Post-RT [^]	6 mo Post-RT [^]	9 mo Post-RT [^]	1 yr Post-RT [^]
Radiotherapy		R	R	(R)						
Informed Consent	X									
Medical History	X	X	X	X	X	X	X	X	X	X
Concurrent meds	X	x	X	X	X	X	X	X	X	X
Adverse Events evaluation		X	X	X	X	X	X	X	X	X
Clinic Visit	X	X	X	X	X	X	X	X	X	X
Pain Assessment	X	X	X	X	X	X	X	X	X	X
CBC/platelets	X	X*			X*		X*			
Serum chemistry ^a	X	X*	X*	X*	X*		X*	X*	X*	X*
Plasma [#]	X						X	X		X
Radiographic imaging ^b	X						X	X	X	X
B-HCG ^c	X									

[^]: Date of post-treatment visit will correspond to the start date (first day) of SBRT

R: Radiotherapy: 10 Gy x 5 fractions, or maximum safe dose to all extracranial sites, and size based SRS

a: Albumin, alkaline phosphatase, total bilirubin, bicarbonate, calcium, chloride, creatinine, glucose, LDH, phosphorus, potassium, total protein, SGOT [AST], SGPT [ALT], sodium.

b: CT of the head, chest, abdomen, and pelvis, and any other pertinent imaging based on clinical situation are required within 28 days of each visit.

c: Serum pregnancy test (women of childbearing potential)

*: CBC and serum chemistry may be obtained per physician discretion following initial assessment. However, it is required to check AST and ALT if SBRT is delivered to liver, at each week of RT, at 1 month post-RT, and at each q3 month follow-up interval (3, 6, 9, 12 months post-RT).

#: For patients who provide consent

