11. MEASUREMENT OF EFFECT

11.1 Antitumor Effects and Endpoints

Although response is not the primary endpoint of this trial, patients with measurable disease will be assessed by standard criteria. For the purposes of this study, patients should be re-evaluated at follow-up visits within one month of completion of radiotherapy, and then subsequently every 3 months for one year. CT of the chest, abdomen, and pelvis, and any other pertinent imaging (e.g. CT or MRI head for brain metastases) are required within 28 days of each follow-up visit.

Response and progression will be evaluated in this study using the international criteria proposed by the Response Evaluation Criteria in Solid Tumors (RECIST) Committee [68]. Changes in only the largest diameter (unidimensional measurement) of the tumor lesions are used in the RECIST criteria.

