11.1.5 Endpoint Definitions

Duration of treated lesion control

Duration of time from start of treatment to the time of local progression at each treated lesion. Local progression is defined as any progressive disease as judged by RECIST criteria of treated lesions

Organ-specific control

Duration of time from start of treatment to the time of development of a new lesion on imaging within an organ in which a lesion was treated with SBRT.

Progression-free survival

Duration of time from start of treatment to time of progression. Progression is defined as any new sites of disease on imaging or any progressive disease by RECIST criteria at initially treated sites of disease (within 80% isodose line).

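### The head-imaging rules contradict each other between entry and follow-up, so a brain lesion already present at baseline could be counted as progression

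*Combined protocol and SAP*

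**What the plan says.** Four places in the protocol deal with head imaging.

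- **Section 3.1.3 (eligibility):** CT of the chest, abdomen and pelvis is needed before registration, but "CT or MRI of the brain is only required in the presence of neurologic symptoms".
- **Section 10, footnote b (Study Calendar):** "CT of the head, chest, abdomen, and pelvis, and any other pertinent imaging based on clinical situation are required within 28 days of each visit". The footnote belongs to the row "Radiographic imaging", which is marked at Pre-Study and at 3, 6, 9 and 12 months.
- **Section 11.1:** follow-up imaging is CT of the chest, abdomen and pelvis plus "any other pertinent imaging (e.g. CT or MRI head for brain metastases) are required within 28 days of each follow-up visit".
- **Schema (follow-up):** "CT chest/abdomen/pelvis q3 months up to 1 year", with no mention of the head.

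On outcome, Section 11.1.5 states: "Progression is defined as any new sites of disease on imaging". Section 11.1.4.2 likewise treats the appearance of new non-target lesions after radiotherapy as overall progressive disease. Section 11.1.2 defines a non-target lesion by its appearing on imaging after radiotherapy. No section says how to classify a lesion found in a region that was not imaged at baseline.

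PFS is a secondary endpoint, estimated at 1 year by Kaplan-Meier (Statistical Methods in the study summary). Patterns of failure are part of objective 1.2.3. Section 12.3 stratifies patients by whether brain metastases are present.

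**The concern.** A lesion can be called new only if the same region was imaged before treatment. Section 3 governs who is registered and Section 10 governs what is done at each visit. Staff who take entry requirements from the first and visit procedures from the second would be following the protocol in both. They would still produce an asymmetric schedule for asymptomatic patients: no head scan at entry, then head CT from month 3. A brain lesion that predates SBRT could then enter the PFS curve as an event at about 3 months and appear among the patterns of failure as a brain relapse.

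Practice could also differ from patient to patient within the 25, so the brain-metastasis stratum would rest on uneven imaging. Section 2.4 says the data may be used to refine eligibility and help with sample-size calculations for later trials, so a spurious cluster of early brain failures could carry forward.

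**Working it through.** **Step 1: set the rules side by side.** The plan states no figure on this point, so the main check is textual. Nothing in the documents ranks the four places. For an asymptomatic patient with no known brain metastases, the possible combinations are:

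| Entry rule followed | Follow-up rule followed | Result |
|---|---|---|
| Calendar | Calendar | Head CT at both; a new lesion is new |
| 3.1.3 | 11.1 / schema | No routine head scan at either; only an indicated scan could reveal an old lesion |
| Calendar | 11.1 / schema | Head CT at entry only; no false new lesion, but later ones may be missed |
| 3.1.3 | Calendar | First head scan at month 3; an old lesion could be scored as new |

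Only the last combination makes the misclassification routine.

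**Step 2: illustrate the size under that combination.** The documents give neither the share q of patients with an unseen brain lesion nor an expected PFS S. I assume q = 2% to 15% and S = 40% or 50% at 1 year. I also assume that no patient had a baseline head scan, that every unseen lesion shows on the first head CT, and that having one is independent of other progression.

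- Patients affected = 25 × q
- Observed PFS = S × (1 − q)
- Share of all progressions that are pre-existing brain lesions = q / [1 − S(1 − q)], shown for S = 40%

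| q | Patients of 25 | PFS if S = 40% | PFS if S = 50% | Share of progressions (S = 40%) |
|---|---|---|---|---|
| 2% | 0.5 | 39.2% | 49.0% | 0.02/0.608 = 3.3% |
| 5% | 1.25 | 38.0% | 47.5% | 0.05/0.62 = 8.1% |
| 10% | 2.5 | 36.0% | 45.0% | 0.10/0.64 = 15.6% |
| 15% | 3.75 | 34.0% | 42.5% | 0.15/0.66 = 22.7% |

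**Step 3: compare with sampling error.** Ignoring censoring, the standard error is √[S(1 − S)/25].

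- S = 40%: √(0.24/25) = 9.8 points, against a largest shift of 40 − 34 = 6.0 points.
- S = 50%: √(0.25/25) = 10.0 points, against 50 − 42.5 = 7.5 points.

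The ratio of shift to standard error is 5q√[S/(1 − S)]. At q = 15% it stays below 1 as long as S is below 64%.

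**Step 4: check what is not affected.** The stopping boundaries in Section 12.1 (2 events in 2 patients, 3 in 14, 4 in 25) give an exact probability of stopping of 78.84% at a true toxicity rate of 20%, which reproduces the stated 78.8%. Imaging does not enter that calculation.

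**The case against.** The strongest reply is that the documents are nearly consistent. Section 3.1.3 covers entry, 11.1 and the schema cover follow-up, and both reserve head imaging for an indication. The outlier is one word, head, in footnote b. The same footnote also covers Pre-Study, so a site that follows the calendar throughout has its baseline head CT. This stands, and it limits the finding. A reader might infer that unseen lesions *would* be counted as progression. The documents support only *could*, because the routine error needs one of the four combinations. It does not remove the finding, because nothing tells a site which combination to use.

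A second reply is that the stakes are small. PFS and patterns of failure are secondary, and Section 12.5 promises description without formal analysis. This also stands. The figures above are probably upper-end. Patients with symptoms or known brain metastases will have had head imaging, not every lesion shows on CT, and some patients with an unseen lesion would have progressed within the year anyway.

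A third concerns eligibility. A reader might infer that symptom-driven imaging at entry is itself an error, because the limit of three brain metastases and the count of one to five lesions cannot be confirmed in an unscanned brain. Section 3.1.3 makes that choice openly. It is an accepted limit of the design, not a contradiction.

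Finally, it is tempting to declare any brain lesion on a first head scan not new. With no time limit, that would remove a genuine symptomatic brain relapse first scanned at month 9 and bias PFS upward.

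**Conclusion.** The point holds as a contradiction in current text that should be reconciled. Section 3.1.3 and footnote b cannot both be the entry rule, and footnote b and Section 11.1 cannot both be the follow-up rule. Following 3.1.3 first and the calendar later opens a route by which pre-existing brain lesions could be scored as progression, and no endpoint rule closes it.

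The size is modest and conditional. On an assumed 2% to 15% of patients with unseen lesions, at most about 0.5 to 4 of 25 are affected, and a PFS of 40% or 50% moves by less than one standard error. Patterns of failure are more sensitive: up to about 23% of progressions at the top of the range, with PFS at 40%. The documents do not support reading this as a demonstrated bias in PFS or as a threat to the primary analysis.

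**What to change.** 1. State one head-imaging rule in 3.1.3, calendar footnote b, 11.1 and the schema, the same at baseline and follow-up. Which rule is for the sponsor to choose.
2. Record for each patient whether the head was imaged at baseline, and by what method, so that the Section 12.3 stratum can be interpreted.
3. Leave the main PFS definition in 11.1.5 unchanged on this point. Do not exclude brain lesions found on a first scan.
4. Add to 12.5 a sensitivity analysis of PFS that sets aside brain-only progression found on the first *routine* head scan of an *asymptomatic* patient who had no baseline head imaging. Flag the same patients in the patterns-of-failure table.

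The cost is wording, one data item and slightly more analysis. If the sponsor aligns to 11.1, no procedure is added, but some asymptomatic brain relapses will be found later. If the sponsor aligns to the calendar, asymptomatic patients gain a head CT at entry that 3.1.3 does not now require.

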3.2 Exclusion Criteria

- 3.2.1 Patients who have had prior chemotherapy, immunotherapy, targeted therapy, or radiotherapy within 1 month of enrollment.
- 3.2.2 Patients who have had any prior bevacizumab, due to case reports suggesting a possible risk of severe toxicity in combination with radiotherapy [58, 59].
- 3.2.3 Patients with radiographic or clinical findings of spinal cord compression or cauda equina syndrome with neurologic deficit thought to be due to malignancy.
- 3.2.4 Patients may not be receiving any systemic anti-cancer agents or other investigational agents during radiation therapy.
- 3.2.5 Patients may not have received prior radiation therapy to a site of recurrence which would require overlap of appreciable radiation dose.
- 3.2.6 Known active invasive malignancy except for renal cell carcinoma and/or non-melanoma skin cancer.
- 3.2.7 Severe, active co-morbidity, defined as follows:
- Unstable angina and/or congestive heart failure requiring hospitalization within the last 6 months prior to registration;
 - Transmural myocardial infarction within the last 6 months prior to registration;
 - Acute bacterial or fungal infection requiring intravenous antibiotics at the time of registration;
 - Chronic Obstructive Pulmonary Disease exacerbation or other respiratory illness requiring hospitalization or precluding study therapy within 30 days prior to registration;
 - Severe hepatic disease, defined as a diagnosis of Child-Pugh Class B or C hepatic disease if the liver is involved with metastatic disease;
 - HIV positive with CD4 count < 200 cells/microliter. Note that patients who are HIV positive are eligible, provided they are under treatment with highly active antiretroviral therapy (HAART) and have a CD4 count ≥ 200 cells/microliter within 30 days prior to registration. Note also that HIV testing is not required for eligibility for this protocol;

3.2.8 Pregnancy or women of childbearing potential who are sexually active and not willing/able to use medically acceptable forms of contraception during protocol treatment or for at least 6 months following treatment; this exclusion is necessary because the treatment involved in this study may be significantly teratogenic.

